## Background

Homecare settings across the United States provide care to more than 5 million patients every year. About one in five homecare patients are rehospitalized during the homecare episode, with up to two-thirds of these rehospitalizations occurring within the first 2 weeks of services. Timely allocation of homecare services might prevent a significant portion of these rehospitalizations. The first homecare nursing visit is one of the most critical steps of the homecare episode. This visit includes an assessment of the patient's capacity for self-care, medication reconciliation, an examination of the home environment, and a discussion regarding whether a caregiver is present. Hence, appropriate timing of the first visit is crucial, especially for patients with urgent health care needs. However, nurses often have limited and inaccurate information about incoming patients, and patient priority decisions vary significantly between nurses.

Our team has developed an innovative clinical decision support system (CDSS) called *Priority for the First Nursing Visit Tool* (PREVENT) to assist nurses in prioritizing patients in need of immediate first homecare nursing visits [18]. PREVENT was developed with rigor, using a strong theoretical foundation (transition theory) [19] and methodology for eliciting experts' decisions to create clinical decision support tools [20]. PREVENT was constructed using data mining, regression modeling, and expert homecare nurses' ratings of example patients who were transitioned from hospital to homecare. The goal was to identify key patient characteristics that are essential to support early homecare admission decision making. Overall, more than 70 patient demographic and clinical characteristics (eg, comorbidities, level and availability of social support, and detailed functional status) were considered for inclusion in the final prediction model from which PREVENT was developed. The final PREVENT CDSS uses 5 factors (including the number of medications, number of comorbid conditions, presence of a wound, presence of a comorbid condition of depression, and patient's functional status) to produce a recommendation on whether a specific homecare patient should be prioritized for the first homecare nursing visit. See

We completed a pilot efficacy study [9] to measure the efficacy of PREVENT, conducted at a large urban hospital in Brooklyn, New York. In collaboration with the Visiting Nurse Service of New York (VNSNY), we enrolled 176 patients admitted to homecare from the hospital during April and May 2016. In the control phase (n=90 patients), we calculated the PREVENT priority score but did not share the score with the homecare admission staff who influence visit scheduling. In the experimental phase, the PREVENT score was shared with the homecare admission staff (n=86 patients). During this phase, patients identified as high priority received their first homecare nursing visit about a half-day sooner as compared with the control phase (1.8 days vs 2.2 days;  $P=.09$ ). Rehospitalizations from

homecare decreased by almost 50% (9.4% point reduction) when comparing the control (21.1%) and experimental phases (11.7%), with a significant difference between the rehospitalization (survival analysis) curves (log-rank  $P = .03$ ). We acknowledge that this pilot study had a relatively small sample size and potentially insufficient adjustment for background variables. However, these results were promising in that high-priority patients received their first homecare visit sooner and overall rehospitalization rates were lower.

## Methods

### Mixed Method Approach

We are using an embedded mixed methods design. We will conduct a pre- and postintervention trial of PREVENT's integration into clinical practice using homecare admissions from two New York City urban hospitals serving diverse racial and ethnic populations. We will use quantitative methods, including logistic regression and survival analysis, to evaluate the effects of the tool on process and patient outcomes. We will utilize qualitative methods integrated with quantitative methods to gain an in-depth insight into technology adoption and implementation.

### Setting

On the basis of our consultations with New York-Presbyterian (NYP) hospitals' leadership and our goal of exploring the effectiveness of the PREVENT system in different settings and among sites serving an ethnically diverse population, we will conduct the study at 2 NYP hospitals: (1) NYP Hospital/Columbia University Irving Medical Center (large academic medical center), a 745-bed adult academic medical center providing emergency, primary, and specialty care in all the major fields of medicine, and (2) NYP Allen Hospital (small community hospital), a 196-bed community hospital serving northern Manhattan, Riverdale, and other communities in the Bronx. As a homecare site, we will use VNSNY—the largest not-for-profit home health agency in the United States serving up to 48,500 patients and health plan members daily.

### Study Intervention: PREVENT

The PREVENT tool will be integrated with the hospitals' electronic health record (EHR) via a locally developed system called iNYP, which integrates with the EHR and provides advanced data review capabilities of all EHR data. iNYP is a Java-based service-oriented web app that builds on Columbia University's 25-year history of clinical information system innovation [28,29]. iNYP is available as a custom tab within the commercial hospital EHR (supplementing the native results review capabilities) and is also accessible from a web browser or a mobile device. iNYP is widely used by most clinicians alongside the EHR, including the homecare admission staff. The PREVENT score will be

calculated automatically from EHR data that populate the patient discharge summary or other parts of the EHR. We have cross-mapped the elements (eg, number of medications and comorbid conditions) needed for the calculation of the PREVENT score to confirm that the required elements are readily available in the EHR system. VNSNY admission staff will receive an auto-populated field within the homecare referral containing the PREVENT recommendation about visit priority, presented as high priority and medium or low priority. Before any data collection, we will test the accuracy of the PREVENT score on the first 50 priority calculations and correct the EHR integration if any mistakes are found.

[figure not shown]
### Standard VNSNY Patient Admission Workflow

During our preliminary work, we determined that the scheduling and assignment unit assumes responsibility for patient admission to the VNSNY. The unit comprises several admission staff members who are involved in the admission processes, including intake coordinators, clinical associate managers, and schedulers. Homecare admission starts with standard homecare referral signed by the referring physician.

The referrals are passed to the intake coordinators (administrative staff) who enter the referral information into the VNSNY EHR system. Next, clinical field managers give patients a welcome call and coordinate the general start of care dates. After that, schedulers identify the date of a first homecare nursing visit. Each geographic location (based on city boroughs and street addresses) is served by several admission staff members.

### Study Workflow

The workflow of PREVENT implementation consists of 3 phases: preintervention phase, intervention phase, and postintervention phase.

## Preintervention Phase

During this phase of the study, 3 research activities will be implemented. First, the PREVENT priority score will be automatically calculated for all the patients referred to VNSNY from the 2 hospitals (step 1). Second, the PREVENT score (and priority recommendation based on the score) will be collected but not shared with homecare admission staff over about 3 months (step 2). Third, after the preintervention phase data are collected, the study team will conduct several 30-min educational sessions for the admission staff about the development and validation of PREVENT and this study (step 3). We will work with the VNSNY scheduling and assignment unit management to identify all the VNSNY staff eligible (15-20 staff) to be exposed to PREVENT's recommendations during the study. We will ensure that each eligible admission staff member undergoes at least one educational session about the study workflow.

## Intervention Phase

To minimize periodical and time effects, the intervention phase will start at both hospitals on the same date. The PREVENT recommendation will be shared with the homecare intake coordinators for about 3 months (step 4). The intake coordinator will enter the PREVENT recommendation into the *special recommendations* field of the VNSNY EHR system. This field stores information about any special programs or services patients should receive in homecare, such as recommendations for frontloading of visits. Next, clinical field managers and schedulers will incorporate the PREVENT priority recommendations in their processes related to visit scheduling and patient prioritization. The field clinician will then conduct the first nursing visit. For cases where patient prioritization was not possible, we will ask the admission staff to document why a priority visit could not happen (such as the patient refused or short staffing; step 5).

## Study Instruments

Qualitative interviews and think-aloud simulations will be guided by two robust interview guides we will develop for this study. The guides will incorporate aspects of the RE-AIM framework dimensions as questions. The guides are as follows: (1) postintervention simulation guide (think-aloud protocol) and (2) postintervention phase interview guide. Each interview guide will include semi-structured open-ended questions to be answered by the admission staff. The *Postintervention phase interview guide* will include questions about PREVENT's perceived usability and ease of use, leadership support, workflow adjustments, adequacy of training sessions, and barriers to implementation such as any

changes the respondent made to his or her regular workflow to use PREVENT's recommendations.

The End-User Computing Satisfaction Instrument [31-33] will be used to quantitatively measure satisfaction. The 12 item instrument measures concepts such as accuracy and ease of use and has been used to evaluate many types of applications, including decision support. A score of 54 corresponds to the 70th percentile. Any concept scoring less than the 70th percentile from either user group will guide future tool revision.

### **Sample Size Calculation**

In this study, we will calculate the PREVENT scores for all patients referred to VNSNY from the 2 hospitals (see study setting) in a 3 month period during the preintervention phase (scores not shared) and a 3 month intervention phase (scores shared) for an estimated total of 2094 patients and 1508 high-priority patients, respectively. This calculation is based on the pilot study rehospitalization decrease.

In the pre-experimental phase of the study, we used secondary data extracted from EHR to calculate PREVENT score. In the experimental phase, we will retrospectively apply the PREVENT algorithm on all patients referred from the two hospitals to homecare settings. We will then use descriptive statistics to identify the number of high and low/medium priority patients (based on PREVENT score) that were referred to homecare. Sample size and justification: Administrative data shows that average monthly referrals to homecare in the first semester of 2018 from New York-Presbyterian Hospital/Columbia University Irving Medical Center and New York-Presbyterian Allen Hospital were 279 and 70 patients, respectively, or a total of 1,396 referrals in a four-month period. Of those, we expect that approximately 50% patients will be classified as high risk by PREVENT. In this study, we will be calculating the PREVENT scores for all patients referred to homecare from these two hospitals in a four-month period during the pre-intervention phase. This sample size is sufficient to estimate the number of high priority patients for the later experimental phase of the study.

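### The stated 1508 high-priority patients imply a 72% share of 2094 that appears nowhere; the only share given, about 50%, yields about 1047

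*Combined protocol and SAP*

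**What the plan says.** All the figures except the pilot rates come from the Sample Size Calculation section of the combined protocol and SAP.

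- The first paragraph describes a 3-month preintervention phase and a 3-month intervention phase, "for an estimated total of 2094 patients and 1508 high-priority patients, respectively". It adds: "This calculation is based on the pilot study rehospitalization decrease".
- The second paragraph says that average monthly referrals from the two hospitals "were 279 and 70 patients, respectively, or a total of 1,396 referrals in a four-month period". Of those referrals, "we expect that approximately 50% patients will be classified as high risk by PREVENT".
- The second paragraph then places the scoring "in a four-month period during the pre-intervention phase". The Preintervention Phase section instead has scores "collected but not shared with homecare admission staff over about 3 months".
- Study Intervention: PREVENT describes the tool's recommendation as "presented as high priority and medium or low priority", so there are two output classes.
- Background gives the pilot rehospitalization rates as 21.1% (control) and 11.7% (experimental). It reports no high-priority proportion.

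No section derives 1508. No alpha, sidedness, power or control rate is given for the sample size.

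**The concern.** The section gives a high-priority count and a high-priority share that do not agree. Because the tool has only two output classes, being high risk by PREVENT can only mean being high priority, so the 50% and the 1508 describe the same class of patient. Both concern referrals from the same two hospitals. A share described as approximately 50% does not stretch to 72%.

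High-priority patients are the group whose visits the tool is meant to bring forward, and Background reports the pilot's visit timing for them. With no alpha, power or subgroup event rate stated, the expected count is the only thing from which a reader can judge how precise a result in that group would be. As written, that count is either 1508 or about 1047.

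**Working it through.** **1. Reproduce the total.** Monthly referrals: 279 + 70 = 349. Four months: 349 x 4 = 1396, as stated. Two 3-month phases: 349 x 6 = 2094, as stated. The total is therefore six months of referrals.

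**2. Try to reproduce the high-priority count.**
- Share implied by the stated count: 1508 / 2094 = 0.720. Conversely, 0.72 x 2094 = 1507.7, which rounds to 1508.
- Count implied by the stated share: 0.50 x 2094 = 1047, or about 524 per phase.
- Gap: 1508 − 1047 = 461, which is 31% of 1508.

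The figure 1047 is also the number of all referrals in one 3-month phase (349 x 3). The two should not be confused.

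**3. Try other phase lengths.**

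| Preintervention + intervention (months) | Referrals | 50% share | 1508 as a share |
|---|---|---|---|
| 3 + 3 | 2094 | 1047 | 72.0% |
| 4 + 3 | 2443 | 1222 | 61.7% |
| 4 + 4 | 2792 | 1396 | 54.0% |
| 4 only | 1396 | 698 | 108% |

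No row gives 1508 at 50%, and every row but the first contradicts 2094. At exactly 50%, 1508 would need 1508 / 0.50 / 349 = 8.6 months of referrals.

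**4. Try the literal reading of *respectively*.** If 2094 belonged to the preintervention phase and 1508 to the intervention phase, one 3-month phase would hold six months of referrals. This reading fails.

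**5. Try 1508 as a sample size calculated from the pilot effect.** Assumptions, since none are stated: two-sided 5%, equal phases, p1 = 0.211, p2 = 0.117, mean rate 0.164, difference 0.094.

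n per phase = [1.96 √(2 x 0.164 x 0.836) + z √(0.211 x 0.789 + 0.117 x 0.883)]² / 0.094²

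- 80% power (z = 0.842): (1.96 x 0.5236 + 0.842 x 0.5194)² / 0.094² gives 243 per phase, 486 in total.
- 90% power (z = 1.282): 324 per phase, 648 in total.
- 99% power: 1132 in total. 99.9% power: 1568 in total.

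One-sided tests, a continuity correction and event-based formulas for a survival comparison do not give 1508 either.

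**6. Size of the consequence.**
- Ratio of standard errors in a high-priority comparison: √(1508 / 1047) = 1.20.
- Minimum detectable reduction in rehospitalization, using the same test at 80% power. No high-priority control rate is given, so a range is shown; 21.1% is the pilot's all-patient rate.

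| Assumed control rate | 754 per phase | About 524 per phase |
|---|---|---|
| 15% | 4.8 points | 5.7 points |
| 21.1% | 5.6 points | 6.6 points |
| 25% | 6.0 points | 7.1 points |
| 30% | 6.4 points | 7.6 points |
| 35% | 6.7 points | 8.0 points |

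- Power for the full pilot effect (21.1% against 11.7%): 99.9% with 754 per phase, 98.5% with about 524.
- An all-patient comparison uses 1047 per phase whichever share is right.

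**The case against.** The strongest counter-argument is that the two figures were never meant as rival estimates. The 50% sits in a separate paragraph about 1,396 referrals over four months, whose stated purpose is to estimate how many high-priority patients to expect later. It could be an early planning guess, and 1508 a later figure based on a measured share of 72%. On that reading the fault is text left without an update and a share without a source, rather than a slip in arithmetic. This is possible, and it is a good reason not to declare either figure wrong. But the documents do not confirm it, and the current section would still hold two figures that cannot both describe the planned study.

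It is also fair to say that the consequence is modest. No section specifies a comparison limited to high-priority patients, and the pilot's rehospitalization rates are for whole phases, so the detectable differences are illustrative. The study scores all referrals over fixed periods, so neither count is an enrolment target. These points limit the weight of the finding without removing the contradiction.

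Finally, the 3-month against four-month discrepancy is a separate inconsistency that does not explain 1508. It belongs here only because the same edit should settle it.

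**Conclusion.** The concern holds. The total of 2094 is confirmed; the 1508 high-priority patients do not follow from the only share the documents state. The discrepancy is 461 patients (1508 against about 1047), and the documents do not show which figure is in error. The one interpretive step is to treat high risk by PREVENT as high priority, which the tool's two output classes support.

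This should be fixed, but it does not threaten the study. Under the assumed test and the pilot's all-patient rates, either count would detect the full pilot effect. What cannot be determined is the expected precision for smaller effects in high-priority patients, where the detectable reduction differs by about one percentage point.

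**What to change.** Rewrite the Sample Size Calculation section around one high-priority share and one preintervention length. Suggested text, with X, N and the source to be filled in by the sponsor:

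> We expect about 2094 referrals over the two phases (349 per month x 6 months). Based on [source], about X% of them (N patients) are expected to be high priority.

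- If X = 50, then N is about 1047 (about 524 per phase), and 1508 is removed.
- If X = 72, then N = 1508 (754 per phase), the source of the 72% is given, and the statement of about 50% is changed to match.

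Drop *respectively*, which wrongly suggests one figure per phase. State one length for the preintervention phase. Three months agrees with 2094 and with the Preintervention Phase section. Four months would make the total 2443 if the intervention phase stays at three months, or 2792 if both phases are four months.

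It would also help to state the expected precision for high-priority patients with its alpha, power and assumed control rate, although that is added detail and not part of the contradiction.

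The cost is wording only. No further patients are needed. If the 50% share is kept, the stated high-priority count becomes smaller.
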